### 10.5.2 Effectiveness Analyses

#### 10.5.2.1 Key Effectiveness Analysis

The key effectiveness endpoint is the change in the convulsive seizure frequency per 28 days between the pre-ZX008 Baseline and OLE Treatment Period. The frequency of convulsive seizures during a given period will be derived from the number and type of events recorded in subject diaries. The seizure frequency per 28 days will be calculated as the number of seizures recorded divided by the number of days in the period and multiplied by 28. The convulsive

seizure frequency will be calculated from all available data collected during either the pre-ZX008 Baseline or OLE Treatment Periods.

Both the mean and median frequency of convulsive seizures will be presented for the pre-ZX008 Baseline Period and the OLE Treatment Period. The significance of the change between periods will be assessed using an analysis of covariance (ANCOVA) model with age group (< 6 years, ≥ 6 years) as a factor and with pre-ZX008 baseline frequency as a covariate. Other factors may be included in the model if they are found to be informative during analyses of the core studies.

Since the ANCOVA relies on assumptions of normality, the key effectiveness endpoint will also be analyzed using a nonparametric method that does not require as stringent assumptions. A test such as the stratified Wilcoxon signed rank test will be used to assess the change from baseline while stratifying by age group.

An additional analysis will be performed to assess the sensitivity of the key effectiveness analysis to changes in dose or type of concomitant AED medications that may occur during the course of the trial. Specifically, the analysis will be repeated with a factor added to the model to indicate whether a subject had a change in prescribed dose or type of concomitant AED medication during the OLE Treatment Period. Further exploratory analyses may be conducted if changes in concomitant AED medication appear to have a significant impact on the effectiveness of ZX008.

Only subjects from Studies ZX008-1501, ZX008-1502, and Cohort 2 of ZX008-1504 will be included in change from baseline analyses of effectiveness. Subjects from Study ZX008-1504 Cohort 1 will be excluded from such analyses since they will enter the OLE Treatment Period without first participating in a baseline period that includes a formal assessment of pre-ZX008 seizure frequency.

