## 2. STUDY OBJECTIVES AND ENDPOINTS

### 2.1 PRIMARY OBJECTIVE

The primary objective of the study is:

- To assess the long-term safety and tolerability of ZX008.

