### 2.2 SECONDARY OBJECTIVES

The secondary objectives of the study are:

- To assess the effect of ZX008 relative to the pre-ZX008 baseline on the following effectiveness measures:
  - The change in the frequency of convulsive seizures from Visit 3 to Visit 8 (ie, Day 31 to Day 365) and for the entire Year 1 treatment period (ie, Visit 1/Day 1 to Visit 8/Day 365)
  - The proportion of subjects who achieve a  $\geq 40\%$ ,  $\geq 50\%$ , and  $\geq 75\%$  reduction in convulsive seizure frequency
  - The longest convulsive seizure-free interval
  - The percentage of convulsive seizure-free days
  - The non-convulsive seizure frequency
  - The convulsive + non-convulsive seizure frequency
- To estimate the incidence of the following on subjects receiving ZX008:
  - Use of rescue medication
  - Hospitalization to treat seizures
  - Status epilepticus (SE)
- To assess the effect of ZX008 relative to the pre-ZX008 baseline on the following QoL measures:
  - Quality of Life in Childhood Epilepsy (QOLCE) score
  - Pediatric Quality of Life Inventory™ (PedsQL score)
  - PedsQL Family Impact module score
  - QoL of the parent/caregiver using the standardized measure of health status (EQ-5D-5L scale)
  - Affective symptoms of the parent/caregiver using the Hospital Anxiety and Depression Scale (HADS)
- To assess the effect of ZX008 on the following QoL measures:
  - Clinical Global Impression – Improvement (CGI-I) rating, as assessed by the principal investigator
  - CGI-I rating, as assessed by the parent/caregiver

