#### Open-Label Extension Treatment Period

The OLE Treatment Period covers the 36 months during which subjects will receive open label treatment with ZX008.

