#### Post-dosing Period

The Post-dosing Period begins immediately at the end of OLE Treatment Period and extends for 2 weeks.

After at least 1 year of treatment in Study 1503 subjects who participated in one of the core studies will transition to a separate extension study (Study 1900) once that study is approved and the study site is initiated. Continuation in a separate extension protocol will be based on benefit/risk and continued eligibility criteria being met. De novo subjects must have participated in this trial for at least 3 months with at least 1 ECHO completed and continue to meet eligibility requirements to be eligible to transition to a separate extension protocol. Alternatively, subjects will transition to commercial product once it is available if they have had an ECHO within 3-6 months before starting commercial drug. For subjects who are entering the separate extension trial or who transition to commercially available drug, post-dosing and cardiac safety follow-up visits are not required in this trial. Subjects who transition to commercially available drug will have follow-up ECHOs within the required timeframe while on commercial drug.

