#### **10.5.2.2 Other Secondary Analyses**

Methods similar to those used for the key effectiveness analysis will also be used to assess the change in frequency of non-convulsive seizures and the composite endpoint of non-convulsive plus convulsive seizures. The proportion of subjects who achieve a ≥40% reduction from baseline in convulsive seizure frequency, along with its 95% CI, will be reported. A similar summary will be reported for the proportion of subjects who achieve a ≥50% reduction from baseline. The analyses will be performed using data collected over the open label OLE Treatment Period.

The longest interval between convulsive seizures will be calculated for each subject over the entire OLE Treatment Period. The median interval will be presented.

Palatability will be assessed through descriptive statistical methods. For example, the percentage of parents or caregivers who consider the medicine's taste and texture to be acceptable to the subject will be presented along with a 95% CI at each time point data are available.

QoL measures will be summarized by descriptive statistic for each time point where they are obtained. Where appropriate, the significance of the change from baseline will be assessed using mixed effects models for repeated measures.

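### The convulsive seizure objective is set on Day 31-365 and Day 1-365, but Section 10 analyses only the whole open-label period of up to 36 months, so the Year 1 question has no planned analysis

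*Protocol*

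**What the plan says.** The primary objective (Section 2.1) is safety: "To assess the long-term safety and tolerability of ZX008". The first effectiveness objective in Section 2.2, repeated in the synopsis, is the change in convulsive seizure frequency relative to the pre-ZX008 baseline. It is given two windows: "from Visit 3 to Visit 8 (ie, Day 31 to Day 365) and for the entire Year 1 treatment period", the latter spelled out as Day 1 to Day 365.

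Section 10.5.2.1 defines the analysis differently: "The key effectiveness endpoint is the change in the convulsive seizure frequency per 28 days between the pre-ZX008 Baseline and OLE Treatment Period". The frequency is the seizure count divided by the days in the period, times 28, and it draws on all available data from the period. Section 10.4 fixes the period's length: "The OLE Treatment Period covers the 36 months during which subjects will receive open label treatment with ZX008". The synopsis methods make the same comparison with the OLE Treatment Period. For the other secondary seizure endpoints, Section 10.5.2.2 adds: "The analyses will be performed using data collected over the open label OLE Treatment Period".

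The analysis set matters here. Section 10.5.2.1 restricts change-from-baseline analyses to subjects from Studies 1501, 1502 and 1504 Cohort 2, and the synopsis excludes de novo subjects from effectiveness analyses. Under Sections 3.1 and 10.4, core-study subjects move to Study 1900 after at least 1 year, once that study is approved and the site is initiated, or to commercial product once available.

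**The concern.** The objective asks about Year 1, both with and without the initial month at 0.2 mg/kg/day. The only analysis specified averages over everything a subject contributes, up to three years. No analysis in Section 10 is cut at Day 365 or starts at Day 31. An SAP author must therefore depart either from Section 2.2 or from Section 10.5.2.1.

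Two things are at stake. First, the reported estimate would not have the time frame that the objective states. Second, in an open-label, single-arm study with interim results already seen, an unresolved conflict leaves room to choose the window after the data are known.

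**Working it through.** **Inputs**
- Objective windows (Section 2.2): Day 31-365 and Day 1-365.
- OLE Treatment Period: 36 months (Section 10.4), 156 weeks (Section 3.3); Visit 16 at Day 1085 (Tables 1, 2 and 7).
- Initial month at 0.2 mg/kg/day: about 30 days (Section 3.1).
- Illustrative reductions (Section 1.3, Study 1 against placebo): 32.4% at 0.2 mg/kg/day and 62.3% at 0.8 mg/kg/day.

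**The plan's own length**
36 × 365.25 / 12 / 7 = 156.5 weeks, against 156 stated. Day 1085 is 1085 / 7 = 155.0 weeks. The figures agree closely; Day 1085 is used below.

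**Overlap of the windows for a 36-month completer**
- Day 31-365: 365 − 31 + 1 = 335 days; 335 / 1085 = 30.9% of the analysed time.
- Day 1-365: 365 / 1085 = 33.6%.
- Outside both windows: 1085 − 365 = 720 days; 720 / 1085 = 66.4%.

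**Spread of record length among core-study subjects**
A completer's record is 1085 / 365 = 3.0 times as long as that of a subject who moves to Study 1900 at Day 365.

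**Share of the record taken by the first month**
- Leaving at Day 365: 30 / 365 = 8.2%.
- Completing at Day 1085: 30 / 1085 = 2.8%.
- Within Day 31-365: 0%.

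**How far the estimates could differ (illustration only)**
Assume a reduction of 32.4% in month 1, 62.3% over Day 31-365, and r after Day 365. The documents give no value for r, so a range of 50% to 75% is shown.
- Day 31-365: 62.3%.
- Day 1-365: (30 × 32.4 + 335 × 62.3) / 365 = 21842.5 / 365 = 59.8%.
- Whole period, completer: (21842.5 + 720 × r) / 1085, which gives 53.3% for r = 50%, 61.5% for r = 62.3% and 69.9% for r = 75%.

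If the effect stays constant after month 1, the completer's whole-period value is within about 1.6 points of the Year 1 value (66698.5 / 1085 − 21842.5 / 365 = 61.47 − 59.84). The answers separate only if the effect, or who is observed, changes after Year 1. The two percentages are placebo-adjusted contrasts, not changes from baseline, and 0.8 mg/kg/day is not the planned maximum for Cohort 2 subjects on stiripentol. They show direction and scale, not an expected result.

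**The case against.** The best defence is that this is a long-term extension with a safety primary objective. An average over all exposure is a legitimate summary, the rate per 28 days already scales for length of follow-up, and Section 10.5 leaves the complete description to the SAP. Much of that stands. The whole-period result is worth having, and adding Year 1 windows needs no new method. But the protocol does not leave the window open: Section 10.5.2.1 names it, and it is not the one in Section 2.2. Scaling by days does not change which days are averaged.

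A reader might infer more than the documents support:
- **That departures of de novo subjects at 3 months distort the estimate.** They are excluded from this analysis. A core-study record ending near Day 90 would be an early withdrawal, at an unstated rate; Section 1.3 gives only 11/330 (3.3%) discontinuing for an adverse event.
- **That the low-dose month dominates short records.** Even at Day 90 it is 30 / 90 = 33%, and Section 3.1 allows an increase from about mid-month for worsening.
- **That changes in concomitant antiepileptic drugs are ignored.** Section 10.5.2.1 repeats the key analysis with a factor for such changes. They are permitted after 6 stable months, so they can also occur within Year 1.
- **That whole-period responder rates contradict the objectives.** The two windows attach only to the first bullet of Section 2.2; the responder and other seizure bullets state none.

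A further caution is sound. Section 1.3 reports a whole-period interim median change of −66.8%. Replacing the whole-period endpoint now with one that omits the low-dose month would be a change made with results in view.

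**Conclusion.** The contradiction holds. Sections 2.2 and 10.5.2.1 specify different windows for the same quantity, and the Year 1 objective has no planned analysis. The firm measure of size is that 66% of a completer's analysed time lies outside both objective windows; this rests only on the visit schedule. The effect on the estimate cannot be fixed from the documents. It is about 1.6 points if the reduction is constant after month 1, and larger only if the effect drifts after Year 1 or departures are related to response. This is a matter to correct rather than one that undermines the study: the objective is secondary, the sample size does not depend on it, and the daily diary already covers both windows.

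**What to change.** In Section 10.5.2.1 and the matching synopsis text, add the change from pre-ZX008 baseline to Day 31-365 and to Day 1-365 as the analyses of this objective. Use evaluable diary days, ending at last dose if earlier, with the ANCOVA and nonparametric methods already planned. State before database lock which of the two is key. Keep and report the whole-period analysis as the long-term result, and disclose that whole-period interim results were known when the text was reconciled. Year 1 responder rates are optional, since the objectives set no window for them.

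Rewriting the objective to match Section 10 would also remove the contradiction. Adding the two windows is preferable because they are already stated and nothing is dropped after results have been seen.

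The cost is one or two extra analyses of data already collected, plus protocol and SAP wording. Early withdrawals will still have unequal follow-up within Year 1.

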#### Effectiveness

The frequency of convulsive seizures during a given treatment period will be derived from the number and type of events recorded in subject diaries. The seizure frequency per 28 days will be calculated as the number of seizures recorded divided by the number of days in the period and multiplied by 28. The convulsive seizure frequency during the OLE Treatment Period will be compared to the pre-ZX008 baseline frequency measured prior to first treatment with ZX008. Both the mean and median change from baseline will be presented and the statistical significance of the change will be assessed using an analysis of covariance (ANCOVA) with baseline frequency as a covariate and age group ( $\leq 6$  or  $\geq 6$  years old) as a factor. Other factors may be included in the model if they are found to be informative during analyses of the core trials. Similar methods will be used to assess the change in frequency of non-convulsive seizures and the composite endpoint of non-convulsive plus convulsive seizures. The percentage of subjects who achieve a  $\geq 40\%$ ,  $\geq 50\%$ , and  $\geq 75\%$  reduction in seizures will be presented along 95% confidence intervals for each percentage. Quality of life measures, such as the QOLCE assessed during the OLE Treatment Period, will be compared to the analogous baseline measure assessed prior to first treatment with ZX008. Subjects who did not participate in one of the core studies will be excluded from analyses of effectiveness and the change over time will be described.

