### 4.1 INCLUSION CRITERIA

Subjects meeting all of the following inclusion criteria may be enrolled into the study:

1. Subject is aged 2 to 18 years inclusive, as of the day of the core study Screening Visit.
2. Subject has satisfactorily completed the core study in the opinion of the investigator and the Sponsor.

NOTE: Those subjects who do not complete the 12-week Maintenance Period of the core study may, on a case-by-case basis, be eligible for entrance after consideration of the circumstances of the early termination and the potential benefit-risk of continued participation in a ZX008 trial. The decision whether to permit open-label extension study participation resides solely with the Sponsor, who may consult with the site investigator, the IPCAB and/or the IDSMC.

3. Subject is male or non-pregnant, non-lactating female. Female subjects of childbearing potential must not be pregnant or breast-feeding. Female subjects of childbearing potential must have a negative urine pregnancy test. Subjects of childbearing or child-fathering potential must be willing to use medically acceptable forms of birth control, which includes abstinence, while being treated on this study and for 90 days after the last dose of study drug.
4. Subject has documented medical history to support a clinical diagnosis of DS, where convulsive seizures are not completely controlled by current antiepileptic drugs.
5. Subject has been informed of the nature of the study and informed consent has been obtained from the legally responsible parent/guardian.
6. Subject has provided assent in accordance with IRB/IEC requirements, if capable.
7. Subject's caregiver is willing and able to be compliant with diary completion, visit schedule and study drug accountability.
8. Subject's parent/caregiver has been compliant with diary completion during the core study, in the opinion of the investigator (eg, at least 90% compliant).
9. Subjects entering from study ZX008-1504 must be receiving a therapeutically relevant and stable dose of CLB and/or VPA, and STP (Cohort 1 dose regimen 3 and Cohort 2 only) for at least 4 weeks prior to screening and are expected to remain stable throughout the study.
10. Subjects who are >18 to ≤35 years of age at the time of screening and did not participate in one of the core studies must meet criteria 3 to 7 above and the following criteria below in order to be considered for participation. Participation is at the discretion of the Sponsor:

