### 7.1 EFFECTIVENESS ASSESSMENTS

For all questionnaires and rating scales, the same evaluator (at the clinical site and parent/caregiver) will complete the assessments for the duration of the study. Substitutions at the clinic with another rater that has established inter-rater reliability is acceptable on an infrequent basis. For the in-clinic questionnaires and rating scales completed by the parent/caregiver, if the same parent/caregiver cannot complete the questionnaire/rating scale at a visit, the questionnaire/rating scale will not be completed. For the diary, the same parent/caregiver will complete all entries throughout the study.

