### **10.4 TREATMENT PERIODS**

#### **Pre-ZX008 Baseline Period**

For subjects who receive ZX008 in Study ZX008-1501, Study ZX008-1502, or Study ZX008-1504 Cohort 2, the pre-ZX008 baseline period is equivalent to the core study pre-

randomization baseline period, ie, the approximately 42-day span just prior to randomization and start of treatment in the core study.

For subjects who receive placebo in Study ZX008-1501, Study ZX008-1502, or Study ZX008-1504 Cohort 2, the pre-ZX008 baseline period begins with the core study pre-randomization baseline period and extends through the entire span of the core study up to the transition period. The pre-ZX008 baseline period for a subject ends when that subject receives their first treatment with ZX008.

Study ZX008-1504 Cohort 1 have a shortened (exploratory) baseline period of approximately 12 days (after the single-dose PK assessment) and this will be used in an exploratory manner.

For de novo subjects, the pre-ZX008 baseline period is the screening period of up to 28 days prior to receiving the first dose.

The baseline frequency of convulsive seizures will be calculated from data collected during the entire length of the pre-ZX008 baseline period.

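### The seizure-frequency formula divides by every day in the period, so a missing diary day counts as seizure-free; percent reduction and responder rates are inflated if OLE diaries are less complete than baseline diaries

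*Protocol*

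**What the plan says.** Section 10.5.2.1 (Key Effectiveness Analysis) takes the count of convulsive seizures from subject diaries and defines the frequency per 28 days as "the number of seizures recorded divided by the number of days in the period and multiplied by 28". The Effectiveness paragraph of the synopsis gives the same rule, word for word. Section 10.5.2.1 then adds that the convulsive "seizure frequency will be calculated from all available data collected during either the pre-ZX008 Baseline or OLE Treatment Periods".

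The rule feeds the main effectiveness result: "The key effectiveness endpoint is the change in the convulsive seizure frequency per 28 days between the pre-ZX008 Baseline and OLE Treatment Period". Under Section 10.5.2.2, similar methods apply to non-convulsive and combined seizure frequency, and the 40% and 50% responder proportions are built on the same frequencies. Section 2.2 and the synopsis also list a 75% threshold.

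On the two periods and their diaries:

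- Section 10.4 sets the baseline for subjects who received ZX008 in Studies 1501, 1502 or 1504 Cohort 2 as "the approximately 42-day span just prior to randomization and start of treatment in the core study". For placebo subjects it runs on through the core study up to the transition period.
- Section 10.4 also says: "The OLE Treatment Period covers the 36 months during which subjects will receive open label treatment with ZX008". Section 3.1 makes this up to 36 months.
- Inclusion criterion 8 (Section 4.1) asks for a caregiver who "has been compliant with diary completion during the core study, in the opinion of the investigator (eg, at least 90% compliant").
- Section 7.1 says: "For the diary, the same parent/caregiver will complete all entries throughout the study". It names no substitute for the diary.

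**The concern.** Numerator and denominator do not cover the same days. A day without an entry adds nothing to the count and one day to the divisor, which amounts to imputing zero seizures. For example, 20 seizures recorded in a 42-day baseline with 4 blank days give 20/42 × 28 = 13.3 under the stated rule, and 20/38 × 28 = 14.7 if only the 38 recorded days are counted.

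The effect on the comparison depends on how completeness differs between periods. The design makes poorer OLE completeness plausible. Core-study diaries had a compliance check at entry to this study, while the OLE asks one caregiver for daily entries over up to three years and states no completion level. Falling completeness would then look like a larger or sustained effect. That matters because Sections 1.3 and 1.10 already describe the reduction as maintained over time. The additional analyses in Section 10.5.2.1 address non-normality and changes in concomitant AEDs; none addresses missing diary days.

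**Working it through.** The protocol has no figure of its own that depends on this rule and could be reproduced, so the check is algebraic.

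**Inputs.** The formula is from Section 10.5.2.1. The 66.8% median reduction at the interim cut-off (Section 1.3) serves only as an example of a true reduction. The missing-day fractions are assumptions: 0% to 10% at baseline, the upper end taken from the 90% example in criterion 8, and 0% to 30% in the OLE. The rate is assumed constant within each period and missingness unrelated to seizures.

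**Percent reduction.** Let *B* be the true baseline frequency, *r* the true fractional reduction, and *mb* and *mo* the missing fractions at baseline and in the OLE. The stated rule returns *B*(1 − *mb*) at baseline and *B*(1 − *r*)(1 − *mo*) in the OLE, so

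displayed reduction = 1 − (1 − *r*)(1 − *mo*)/(1 − *mb*).

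| True reduction | Baseline missing | OLE 0% | OLE 10% | OLE 20% | OLE 30% |
|---|---|---|---|---|---|
| 0% | 0% | 0.0 | 10.0 | 20.0 | 30.0 |
| 0% | 10% | −11.1 | 0.0 | 11.1 | 22.2 |
| 66.8% | 0% | 66.8 | 70.1 | 73.4 | 76.8 |
| 66.8% | 10% | 63.1 | 66.8 | 70.5 | 74.2 |

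For example, 1 − 0.332 × 0.8 = 73.4%, and 1 − 0.332 × 0.8/0.9 = 70.5%. Equal fractions cancel; more missing at baseline reverses the sign of the bias.

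**Responder threshold.** A subject is displayed as a 50% responder once the true reduction reaches 1 − 0.5(1 − *mb*)/(1 − *mo*):

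- 0% baseline, 20% OLE: 1 − 0.5/0.8 = 37.5% is enough.
- 10% baseline, 20% OLE: 1 − 0.45/0.8 = 43.8% is enough.
- 10% baseline, 0% OLE: 1 − 0.45 = 55.0% is needed.

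**Absolute change**, which is how the key endpoint is worded. Assume a true baseline of 20 per 28 days (not in the documents) and *r* = 66.8%. The true OLE value is 6.64 and the true change is −13.36.

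- 0% baseline, 20% OLE: 5.31 − 20 = −14.69, overstated.
- 10% in both: 5.98 − 18 = −12.02, understated.
- 10% baseline, 20% OLE: 5.31 − 18 = −12.69, still understated.

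In general the displayed change differs from the true one by *B*[*mb* − (1 − *r*)*mo*]. The absolute benefit is overstated only if *mo* exceeds *mb*/(1 − *r*), which here is 0.10/0.332, or about 30%, when 10% is missing at baseline.

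**With recorded days as the denominator**, both period frequencies return to their true values under the same assumptions, and so do the percent and absolute changes.

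**The case against.** Several points on the other side have force.

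- *The direction is not fixed.* A reader might infer that the rule always favours the drug. It does not: missing baseline days work against it, and the absolute change can be understated even when the OLE has more gaps.
- *No missing-diary rate is given.* The 20% and 30% figures are scenarios. Carrying the 90% example unchanged into the OLE would give no bias in percent reduction. For the same reason, the documents do not support inferring that the interim 66.8% is itself inflated.
- *There are diary controls.* Criteria 7 and 11 ask for a caregiver able to comply. Diaries are collected and reviewed at clinic visits (Sections 6.1.3 to 6.1.5), the investigator checks completeness (Section 9.1), and persistent noncompliance is a ground for discontinuation (Section 4.4). These make large losses less likely but do not change the divisor.
- *The contrast between a short baseline and a long OLE is partial.* The 42-day baseline applies only to subjects who received ZX008 in the core study. Placebo subjects add roughly the 14 or 15 treatment weeks of the core study.
- *The formula's reach is limited.* A reader might extend the bias to the longest seizure-free interval and the percentage of seizure-free days. The protocol does not compute either from this formula, so they are not part of this point.
- *Missing-data detail usually belongs in the SAP*, and Section 10.5 defers the full methods there. This does not remove the point. The protocol does not leave the divisor open; it states it twice. The reference to all available data says which data are used, not what to divide by. An SAP using diary days would depart from the protocol text, and one following the text would carry the bias.

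**Conclusion.** The point holds in conditional form. Read as written, the protocol counts each missing diary day as seizure-free, which biases frequency downward in each period that has gaps. Percent reduction and responder rates are overstated only if OLE diaries are less complete than baseline diaries. The design makes that plausible, but the documents do not show it.

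The illustrated inflation at 20% OLE missing is 20 to 11.1 percentage points when there is no true effect, and 6.6 to 3.7 points at a true 66.8% (73.4 − 66.8 and 70.5 − 66.8), for 0% to 10% missing at baseline. These sizes rest on the assumed missing fractions, a constant rate within each period, and missingness unrelated to seizures.

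The primary objective is long-term safety and effectiveness is secondary, so this is a correction that should be made rather than one on which the study depends.

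**What to change.** In Section 10.5.2.1 and in the Effectiveness paragraph of the synopsis, change the divisor to the number of days in the period with an evaluable diary entry, meaning seizures recorded or a no-seizure day confirmed. Apply it to both baseline and OLE, count only seizures on those days, and report diary completeness by period.

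The cost is a sentence in two places, a small programming change, and possibly a less favourable estimate. The new rule is not assumption-free: if caregivers tend to leave quiet days blank, dividing by recorded days overstates frequency. The all-days calculation should therefore be kept as a sensitivity analysis, so that the reader can see how far the result depends on what missing days are taken to mean.
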